7.6 Permitted Medications and Procedures

We do not anticipate significant drug interactions with the study products at this time, therefore, if clinically necessary, participants can be initiated on other medications for intercurrent illnesses that might occur during their study participation.

7.7 Prohibited Medications and Procedures

We do not anticipate significant drug interactions with the study products at this time. Participants that enroll in the study agree to not participate in other studies of investigational drugs. In addition, they should not participate in studies that require frequent blood sample collection.

Use of systemic corticosteroids (long term use), immunosuppressive anti-cancer, interleukins, systemic interferons, systemic chemotherapy within 6 months of study enrollment is not permitted. Short term use of systemic steroids (e.g. steroid taper for allergic or infusion reactions or asthma exacerbation) is permitted.

7.8 Precautionary Medications and Procedures

We do not anticipate significant drug interactions with the study products at this time. Participants that enroll in the study agree to not participate in other studies of investigational drugs. In addition, they should not participate in studies that require frequent blood sample collection.

7.9 Required Medications

Not applicable. Participants will be advised and encouraged to initiated ART within 4 weeks after 3BNC117-LS and 10-1074-LS infusions within 4 weeks of receiving 3BNC117-LS and 10-1074-LS infusions, or sooner if: VL fails to decrease by $>0.5 \log_{10}$ copies/ml within 2 weeks of antibody infusions, VL increases $> 0.5 \log_{10}$ copies/ml between weekly measurements or significant T-cell decline (confirmed CD4+ T cell count < 200 cells/ μ l) is noted.

7.10 Rescue Medications

If volunteers develop grade 3 acute infusion reaction, an immediate hypersensitivity reaction or a life-threatening event during study drug administration, the infusion will be discontinued and will not be reinitiated (see Section 6.1.7.1). Rescue medications, including acetaminophen, diphenhydramine and glucocorticoids will be available at the clinical sites for use if clinically indicated.

8 DATA ANALYSIS

8.1 Analysis of Safety, PK and Antiretroviral Effects

Primary Outcomes

- **Safety:** The safety population will include all participants who receive a dose of 3BNC117-LS and 10-1074-LS. A baseline measurement and at least one laboratory, vital sign, or other safety-related measurement obtained after 3BNC117-LS and 10-1074-LS dosing may be required for inclusion in the analysis of a specific safety parameter.

The number and percentage of participants experiencing one or more AEs will be summarized by relationship to study drug, and severity. AEs will be summarized by the number and percentage of participants who experienced the event, according to system organ class (SOC) and preferred term. AEs will also be summarized by severity grade and by relationship to study drug according to the DAIDS AE Grading Table, corrected v2.1 (July 2017). The CTCAE v5.0 grading scale will be used for reporting and grading adverse events occurring within 24 hours of the start of 3BNC117-LS and/or 10-1074-LS infusions that are considered infusion reactions or cytokine release syndromes. Changes in hematology, chemistry, and other laboratory values will be summarized descriptively. Changes will be calculated relative to the values collected at baseline.

- **Pharmacokinetic parameters:** will be calculated using standard non-compartmental analysis methods. Pharmacokinetic parameters, including AUC, Cmax, T_{1/2}, Tmax, clearance and others will be summarized. Pharmacokinetic parameters will be examined to correlate exposure with safety and pharmacokinetics parameters, and variance based on population intrinsic factors such as weight and gender will be explored.
- **Antiretroviral activity:** The magnitude of change in plasma HIV-1 RNA levels from baseline will be evaluated. Plasma HIV-1 RNA levels will be evaluated prior to and at multiple time points following 3BNC117-LS and 10-1074-LS infusions and the log copies/ml reduction in HIV-1 RNA level from baseline will be calculated.

Secondary Outcomes

- Anti-3BNC117-LS and anti-10-1074-LS antibodies: The frequency of induced anti-3BNC117-LS or anti-10-1074-LS antibodies will be reported. Occurrence of ADA will be evaluated by a three-tiered approach using validated screening and confirmatory assays, followed by tittering of responses to determine if responses were treatment-induced or treatment-boosted.

Other Exploratory Measurements

- Genotyping and phenotyping of HIV isolates will be performed to analyze the induction of escape mutations following 3BNC117-LS and 10-1074-LS infusions in viremic individuals enrolled in the study. Specifically, we will perform single genome amplification (SGA) of plasma viruses to define the relationship between individual responses to antibody therapy and circulating virus sensitivity to the antibodies. CMV-promoter-based pseudoviruses will be constructed from selected SGA sequences and tested for bNAb sensitivity in a TZM-bl assay. Results will be descriptive.

Continuous data will be summarized by descriptive statistics, including the sample size, mean, standard deviation, median and range. Categorical data will be summarized by the number and percentage of participants.

The analysis of study data will be primarily descriptive, with emphasis on tabular and graphical displays. Summary statistics will be calculated, along with point and interval estimates of solicited and unsolicited adverse events. The pharmacokinetic profiles of a single administration of 3BNC117-LS in combination with 10-1074-LS will also be determined. This study is exploratory, and any statistical inferences will be hypothesis generating and not confirmatory.

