3.12 Outcomes

Primary Outcomes:

- The occurrence of treatment-related solicited and unsolicited grade 3 and serious adverse events (including confirmed laboratory abnormalities).
- The pharmacokinetic profile (including: peak concentrations, half-life, area under curve and clearance rate) of 3BNC117-LS and 10-1074-LS, when administered intravenously and in combination to viremic HIV-infected individuals.
- The decline in plasma HIV-1 RNA level after 3BNC117-LS plus 10-1074-LS intravenous infusions in viremic HIV-infected individuals through week 4 after infusions.

Secondary Outcomes:

- Proportion of individuals with treatment-induced ADA against each mAb and magnitude of the response.
- The rate of adverse events and confirmed laboratory abnormalities that occur during the study follow up period after 3BNC117-LS and 10-1074-LS administration.

Exploratory Outcomes:

[figure not shown]
- Time until return of viremia to baseline levels in participants, who elect to remain off ART after 4 weeks.
- Decline in plasma viremia after antibody infusions across 3BNC117-LS and 10-1074-LS IC₅₀ and IC₈₀ cut points determined by PhenoSense assay or other assays (e.g. bulk PBMC cultures or Q2VOA followed by TZM/bl assay).
- Phenotypic and genotypic analysis of baseline and escape viruses that might arise after single infusions of 3BNC117-LS and 10-1074-LS in viremic HIV-infected individuals.
- Proportion of participants with reduction in half-life or antiviral activity concomitant with ADA.
- Relationship of adverse events to ADA.
- Frequency and magnitude of HIV-1 specific T cell responses and serum neutralizing activity against a multi-clade panel of HIV-1 pseudoviruses, following 3BNC117-LS and 10-1074-LS infusions.
- Gene expression profiles by single RNA sequencing of HIV-1 infected CD4+ T cells.

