6.1.3 Study Drug Administration Visit

Prior to administration of the investigational product(s), site personnel will:

- Review the informed consent form administered at the screening visit with the participant;
- Answer any questions about the study;
- Review interim medical history (including concomitant medications);
- Review safety laboratory data;
- Perform a directed physical examination including weight, vital signs (pulse, respiratory rate, blood pressure and temperature) and any further examination indicated by history or observation;
- Collect blood and urine specimens for all tests as indicated in the Time of Events Schedule (**Appendix A**);
- Perform pregnancy and safer sex counseling;
- Perform a serum pregnancy test for all female volunteers of child-bearing potential and obtain results prior to drug infusion.
- Perform baseline assessment and record any systemic symptoms;
- 3BNC117-LS and 10-1074-LS will be prepared for administration according to **Appendix C**;

Antibody Administration:

- 3BNC117-LS will be administered via a peripheral vein over 30 minutes. The IV line will be flushed with normal saline after all the contents of the infusion bag are administered.
- 10-1074-LS will be administered after 3BNC117-LS infusion is completed and the line is flushed with normal saline. It will also be administered via a peripheral vein over 30 minutes. The IV line will be flushed with normal saline after all the contents of the infusion bag are administered.
- If participants develop grade 3 acute infusion reaction, an immediate hypersensitivity reaction or a life-threatening event during study drug administration, the infusion will be

discontinued and will not be reinitiated (see Section 6.1.7.1). If the acute infusion reaction occurs during 3BNC117-LS infusion, 10-1074-LS infusion will not be infused.

- Participants will be observed for adverse reactions at the study site for 1 hour after the end of the 10-1074-LS infusion. Presence or absence of adverse events will be recorded at 1 hour post infusion.
- Vital signs (pulse, respiratory rate, blood pressure and temperature) will be monitored before administration, at the end of each infusion, 30 minutes (+/- 10min) post final infusion, and at 1 hour (+/- 10 min) post final infusion;

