6.1.6 Discontinuation of Study Drug Infusions and/or Participant Withdrawal from Study

6.1.6.1 Discontinuation of Study Drug Infusion

Antibody intravenous infusion will be discontinued for any of the following reasons:

1. Grade 3 acute infusion reactions that occur during infusion.
2. Any immediate hypersensitivity reaction (such as urticarial rash; bronchospasm; laryngeal edema; anaphylaxis; syncope).
3. Life threatening medical event during 3BNC117-LS or 10-1074-LS infusion.

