8.4 Participant Enrollment and Follow-Up

The total number of evaluable participants in the study will be 5 to 10.

An over-enrollment of 2 participants will be allowed if participants drop-out prior to week 4. Participants who are discontinued from the study due to AEs will not be replaced. Additional participants will be enrolled after study withdrawal is confirmed. If a participant drops out after receiving 1 or both study drugs, he/she will be invited to return every 4 weeks, for at least 3 months after antibody infusion, for safety monitoring only.

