15.8 Toxicity Management and Stopping Rules

A dose limiting toxicity (DLT) will be defined as any adverse event of Grade 3 or greater toxicity, if the study investigators recognize a probable or definite attribution to 3BNC117-LS and/or 10-1074-LS mAb. Clinically significant grade 3 laboratory abnormalities must be confirmed by a repeat test, obtained as soon as possible following the initial result.

Investigators will promptly notify the PI and Sponsor at The Rockefeller University in the event of any DLT.

In the case of two or more DLTs, further enrollment or infusions of 3BNC117-LS and/or 10-1074-LS will not occur until investigators and SMC review the events and all available safety data. Enrollment will stop but participants will continue to be monitored by the study investigators. The SMC members will make a recommendation to the principal investigators regarding the continuation of the trial.

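### Read literally, the safety population leaves out a participant who gets no 10-1074-LS because of an acute infusion reaction during 3BNC117-LS

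*Combined protocol and SAP*

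**What the plan says.** Section 8.1 states: "The safety population will include all participants who receive a dose of 3BNC117-LS and 10-1074-LS". The next sentence uses the same joint wording for individual parameters: a baseline value and a laboratory, vital-sign or "other safety-related measurement obtained after 3BNC117-LS and 10-1074-LS dosing may be required for inclusion in the analysis of a specific safety parameter". No other section defines the safety population.

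The infusions are sequential. Section 6.1.3 says "10-1074-LS will be administered after 3BNC117-LS infusion is completed and the line is flushed with normal saline", and then "If the acute infusion reaction occurs during 3BNC117-LS infusion, 10-1074-LS infusion will not be infused". The first trigger for stopping an infusion in Section 6.1.6.1 is "Grade 3 acute infusion reactions that occur during infusion"; the others are immediate hypersensitivity and life-threatening events.

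The first primary outcome in Section 3.12, repeated in the synopsis, is "The occurrence of treatment-related solicited and unsolicited grade 3 and serious adverse events (including confirmed laboratory abnormalities". The dose-limiting toxicity definition in Section 15.8 covers "any adverse event of Grade 3 or greater toxicity".

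Other parts of the plan foresee exposure to a single antibody. Section 8.4 begins its provision for continued safety visits with "If a participant drops out after receiving 1 or both study drugs". Section 8.1 itself grades infusion reactions after either or both infusions, and Section 8.2 states its safety bound for events related to either or both antibodies.

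**The concern.** A participant who has a grade 3 acute infusion reaction during 3BNC117-LS never starts 10-1074-LS, and so has not received both products. Taken at its word, Section 8.1 leaves that person out of the safety population. If the reaction is judged related, it is also an event of the kind the primary safety outcome counts. The person leaves both numerator and denominator because of the outcome, which moves the reported rate down.

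Section 12 names infusion or hypersensitivity reaction as the main safety concern with monoclonal antibodies in general, so this is not a remote category of event. With 5 to 10 participants, a single person makes the difference between reporting no related grade 3 event and reporting one.

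**Working it through.** **Inputs.** 5 to 10 participants, and a one-sided 95% upper bound for the related grade 3 rate with zero events of 25.9% to 45.1% (Section 8.2). Order of infusion and the withholding rule (Section 6.1.3). No replacement of participants discontinued for adverse events (Section 8.4).

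**Step 1: reproduce the plan's figures.** With zero events the exact bound is 1 − 0.05^(1/n).
- n = 10: 1 − 0.05^(1/10) = 25.9%.
- n = 5: 1 − 0.05^(1/5) = 45.1%.

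Both agree with Section 8.2.

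**Step 2: apply the definition to one participant.** The participant starts 3BNC117-LS and has a grade 3 acute infusion reaction; the infusion stops and 10-1074-LS is not given. The condition of having received both antibodies fails. Section 8.1 does not say whether a partial infusion counts as a dose, but that does not matter here because the second antibody is never started. It would matter for a stop during the second infusion.

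**Step 3: effect on the report.** Assume that exactly one participant is stopped in this way, that the event is related and grade 3 or serious, that nobody else has a primary event, and that the participant is not replaced. For zero events use the formula in Step 1. For one event in n, the exact bound is the p that solves (1 − p)^n + n·p·(1 − p)^(n−1) = 0.05.

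| Enrolled | Literal definition | Upper bound | Any exposure counted | Upper bound |
|---|---|---|---|---|
| 10 | 0/9 = 0% | 28.3% | 1/10 = 10% | 39.4% |
| 5 | 0/4 = 0% | 52.7% | 1/5 = 20% | 65.7% |

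**Step 4: the other direction.** If the person left out has no primary event (for example a one-antibody recipient who drops out for another reason), including that person changes 0/9 (upper bound 28.3%) to 0/10 (25.9%). The corrected definition can therefore make the reported rate look better as well as worse.

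**Step 5: how likely is such a case?** The documents give no rate of first-infusion stops. For an assumed per-person rate q, the chance of at least one is 1 − (1 − q)^n.

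| Assumed q | n = 5 | n = 10 |
|---|---|---|
| 1% | 4.9% | 9.6% |
| 2% | 9.6% | 18.3% |
| 5% | 22.6% | 40.1% |
| 10% | 41.0% | 65.1% |

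These values of q are illustrations, not estimates from the programme.

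**The case against.** The strongest reply is that the joint wording is loose drafting. The two antibody names joined by *and* serve throughout as the name of the study treatment. The sentence says who is included and does not say that only they are. Wherever the plan considers exposure to one antibody (Sections 8.1, 8.2, 8.4, 15.1 and 15.8), it covers it, and the synopsis has no both-antibody restriction. This stands as evidence of intent. A reader might infer that the sponsor chose to leave reactors out; the documents do not support that. But intent inferred from other sections does not change the only definition given, and leaving it means deciding whether a reactor counts after the data are seen.

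A reader might also infer that any stopped infusion hides a primary event. That goes too far. Section 6.1.6.1 stops the infusion for any immediate hypersensitivity reaction, with no grade threshold, so a low-grade, non-serious reaction could end dosing without being a primary event. Section 6.1.3 states expressly that 10-1074-LS is withheld only for an acute infusion reaction; for the other two triggers it says that the infusion is discontinued.

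Nor is participant protection at stake. Events are collected and graded whatever the analysis set, and committee review and pausing under Sections 15.1 and 15.8 act on events. No decision rule uses the safety-population rate, and Section 8.1 calls the analysis primarily descriptive and its inferences not confirmatory. To date, Section 3.8 reports no grade 3 or serious adverse events deemed possibly related to the LS antibodies. These points limit the consequence to what is tabulated. They do not remove it, because Section 8.1 also commits to point and interval estimates of adverse events.

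**Conclusion.** The point holds as a defect of definition that should be fixed. Section 8.1, read with Section 6.1.3, makes membership of the safety population depend on the safety outcome, and it conflicts with the plan's own provisions for one-antibody recipients. In the case worked above, one event would be reported as 0/9 instead of 1/10, or 0/4 instead of 1/5, with upper bounds of 28.3% instead of 39.4% and 52.7% instead of 65.7%. Those figures rest on one first-infusion stop that is a related grade 3 or serious event, no other primary event, and no replacement.

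The effect is confined to analysis and reporting. It does not touch the sample-size figures in Section 8.2, event collection, committee review or the stopping rules.

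A smaller wording matter sits beside it. Read literally, the primary outcome does not count a related, non-serious grade 4 event. A reader might infer that such events go unreported. They do not: Section 8.1 tabulates adverse events by severity and relationship, the secondary outcome covers all adverse events, and Section 6.2.9.2 reports clinically significant laboratory abnormalities of grade 3 or above. Only the primary-outcome label misses them. The dose-limiting toxicity definition serves a different purpose and need not match an endpoint, though the difference shows that the label is loose.

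**What to change.** 1. In Section 8.1, define the safety population as *all participants who receive any amount of 3BNC117-LS and/or 10-1074-LS*. This also settles how partial infusions are treated.
2. In the next sentence, ask for a measurement obtained *after the start of 3BNC117-LS and/or 10-1074-LS dosing*. Without this edit the same participant could still drop out of the laboratory or vital-sign summaries.
3. As a minor further edit, word the primary safety outcome in the synopsis and Section 3.12 as *grade 3 or higher, or serious*.

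The cost is two wording edits for the population and one phrase, in two places, for the outcome. No dosing rule, stopping rule, sample size or data collection changes. The reported rate may move in either direction, as Steps 3 and 4 of the working show.

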8.2 Sample Size Considerations

Five to 10 evaluable participants are sought. The total number of screened participants to achieve 5 to 10 evaluable participants is estimated to be 15 to 30. Replacement for 2 participants lost to follow up prior to week 4 will be allowed.

Safety:

We expect that the administration of a single infusion of 3BNC117-LS in combination with 10-1074-LS will be generally safe and well tolerated.

The sample size of 5 to 10 participants receiving 3BNC117-LS and 10-1074-LS in combination will provide 95% probability of observing a treatment-related AE that would occur in 26% to 45% or more of treated participants. If none of the participants experiences a grade 3 AE related to 3BNC117-LS and/or 10-1074-LS, the one-sided 95% upper confidence bound for the rate of AEs in the population is 25.9% to 45.1%.

Pharmacokinetics:

Based on the pharmacokinetic profile of VRC01LS in humans, another anti-HIV-1 antibody targeting the same gp120 site as 3BNC117-LS, 3BNC117-LS and 10-1074-LS data in NHP, and preliminary 3BNC117-LS and 10-1074-LS data in humans, it is expected that the half-lives of 3BNC117-LS and 10-1074-LS will be approximately 3-fold higher than the unmodified antibodies. Therefore, we expect that 3BNC117-LS will have a $t_{1/2}$ in humans of approximately 70 days. Similarly, we expect that 10-1074-LS will have a $t_{1/2}$ in humans of approximately 90 days.

In a previous study with 10-1074, the mean elimination half-life of approximately 24 days (SD 6.6 days) in HIV-uninfected and 12.8 days (SD 4.9 days) in viremic HIV-infected individuals (Caskey et al 2017). 3BNC117 has a mean elimination half-life of approximately 17.6 days (SD 5.7 days) in HIV-uninfected and 9.6 days in viremic HIV-infected individuals (SD 2.9 days) (Caskey et al., 2015). PK parameters were maintained when the two antibodies were administered in combination.

The margins of error at 95% confidence level for estimating the mean elimination half-life of either mAb, based on standard deviations in the range of 4.5 to 6.5 days using the available pharmacokinetics data of 3BNC117 and 10-1074, and 5 or 10 participants are included in **Table 3**.

Table 3. Margin of Error at 95% Confidence Level for Estimating the Mean Elimination Half-life of 3BNC117-LS and 10-1074-LS

Standard Deviation (days)	95% margin of error (+/- days) n = 5	95% margin of error (+/- days) for n = 10
4.5	3.9	2.8
5	4.4	3.1
5.5	4.8	3.4
6	5.3	3.7
6.5	5.7	4.0

Antiviral activity:

Single infusions of 3BNC117 and 10-1074, dosed at 30 mg/kg, led to an average decline in viremia of $1.48 \log_{10}$ copies/ml (range = 0.8-2.5 and SD = $0.6 \log_{10}$ copies/ml) (Caskey, Klein et al. 2015) and $1.52 \log_{10}$ copies/ml (range = 0.9-2.06 and SD = $0.4 \log_{10}$ copies/ml) (Caskey, Schoofs et al. 2017). The average decline in viral load for 4 viremic participants who received one or three infusions of the 3BNC117 and 10-1074 combination was $2.05 \log_{10}$ copies/ml (range = 1.58-2.57 and SD = $0.7 \log_{10}$ copies/ml) (Bar-On et al. 2018).

A recent study, ACTG NWCS 413, utilized the Monogram PhenoSense assay to estimate baseline 3BNC117 and 10-1074 sensitivity of HIV pseudovirions that express envelope proteins representative of the quasispecies of proviral HIV-1 DNA in PBMCs. For 3BNC117, the median IC₅₀ was $0.087 \mu\text{g}/\text{mL}$ (Q1, Q3 of 0.061, 0.183) and median IC₈₀ was $0.301 \mu\text{g}/\text{mL}$ (Q1, Q3 of 0.206, 0.680); whereas for 10-1074, the median IC₅₀ was $0.044 \mu\text{g}/\text{mL}$ (Q1, Q3 of 0.020, 0.222) and median IC₈₀ was $0.184 \mu\text{g}/\text{mL}$ (Q1, Q3 of 0.066, 1.578). 61% (37/61) of the participants' virus swarms fell under the predicted sensitivity threshold of IC₈₀ < $1 \mu\text{g}/\text{mL}$ to both 3BNC117 and 10-1074, with 77% and 74% falling under this level for 3BNC117 only and 10-1074 only, respectively, and 89% for either antibody.

Table 4 shows the minimum average decline in plasma HIV-1 RNA levels (\log_{10} copies/ml) that can be detected with 80% power and a two-sided 0.05 test, assuming a standard deviation of 0.7 (\log_{10} copies/ml) from the 3BNC117 plus 10-1074 data. If 4 out of 10 participants harbor viruses sensitive to both antibodies, the minimum average decline in plasma HIV-1 RNA levels that can be detected with 80% power and a two-sided 0.05 test is $1.49 \log_{10}$ copies/ml. If we assume 60% of the participants will be sensitive to either antibody, the probability of observing at least 4 responders (HIV-1 RNA $\geq 0.5 \log_{10}$ copies/ml) out of up to 10 enrolled participants who receive 3BNC117-LS and 10-1074-LS is 0.95.

Table 4. Minimum average decline in plasma viremia that can be detected for varying sample sizes

N	SD (\log_{10} copies/ml)	two-sided test alpha =0.05	
		Minimum average decline in plasma HIV-1 RNA (\log_{10} copies/ml)	Effect size
3	0.7	2.29	3.26
4	0.7	1.49	2.13
5	0.7	1.18	1.68
6	0.7	1.00	1.43
7	0.7	0.89	1.27
8	0.7	0.81	1.16
9	0.7	0.75	1.07
10	0.7	0.70	1.00

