3.4 Clinical Experience with Fc-modified Antibodies to Enhance Binding to the FcRN Receptor

VRC01LS is another human anti-HIV-1 CD4 binding site antibody that has been modified in the Fc region to include the LS substitutions (M428L/N434S). Like 3BNC117-LS, it is being evaluated for HIV-1 therapy and prevention. VRC01LS is being evaluated in four ongoing clinical studies in HIV-infected (NCT02840474) and HIV-uninfected adults (NCT02599896, NCT02797171), and in

infants (NCT02256631). VRC01LS showed good safety profile in a first-in-human study in HIV-uninfected participants. A total of 37 participants were administered VRC01LS, and received one or three intravenous infusions or subcutaneous injections at 5, 20 or 40 mg/kg dose levels. There were no SAEs or DLTs. Mild malaise and myalgia were the most common adverse events (AEs). There were six AEs assessed as possibly related to VRC01LS administration, and all were mild in severity and resolved during the study. The mean (\pm SD) serum concentration 12 weeks after one IV administration of 20 mg/kg or 40 mg/kg were 180 ± 43 μ g/mL (n = 7) and 326 ± 35 μ g/mL (n = 5), respectively. The mean (\pm SD) serum concentration 12 weeks after one IV and SC administration of 5 mg/kg were 40 ± 3 μ g/mL (n = 2) and 25 ± 5 μ g/mL (n = 9), respectively. VRC01LS clearance rate was 36 ± 8 mL/d with an elimination half-life of 71 ± 18 days. VRC01LS retained its expected neutralizing activity in serum, and anti-VRC01 antibody responses were not detected (Gaudinski, Coates et al. 2018).

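### Table 3 overstates the precision of the mean half-life: it uses the normal quantile at n = 5 and 10, and parental-antibody SDs for LS antibodies expected at 70 and 90 days

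*Combined protocol and SAP*

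**What the plan says.** Section 8.2 (Pharmacokinetics) expects that the "half-lives of 3BNC117-LS and 10-1074-LS will be approximately 3-fold higher than the unmodified antibodies". From this it derives a half-life for 3BNC117-LS "in humans of approximately 70 days", and about 90 days for 10-1074-LS. It then quotes parental half-lives and SDs in HIV-uninfected and in viremic people.

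Table 3 is titled "Margin of Error at 95% Confidence Level for Estimating the Mean Elimination Half-life of 3BNC117-LS and 10-1074-LS". Its SDs run from 4.5 to 6.5 days and are described as "based on standard deviations in the range of 4.5 to 6.5 days using the available pharmacokinetics data of 3BNC117 and 10-1074". The columns are n = 5 and n = 10, in line with the statement that "Five to 10 evaluable participants are sought". The margins are 3.9, 4.4, 4.8, 5.3 and 5.7 days at n = 5, and 2.8, 3.1, 3.4, 3.7 and 4.0 days at n = 10. The quantile is not named.

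Three other places bear on this:
- Section 3.4 reports VRC01LS, another LS antibody, "with an elimination half-life of 71 ± 18 days".
- Section 3.7 gives half-lives for the parental antibodies in combination, in HIV-uninfected people: 18.4 ± 2.5 days (3BNC117) and 22.3 ± 1.5 days (10-1074).
- Section 3.8 gives preliminary data for the LS antibodies. The half-life of 3BNC117-LS exceeds 60 days in HIV-uninfected people, 3.9-fold the parental value. That of 10-1074-LS appears to exceed 90 days.

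**The concern.** Half-life is part of a primary outcome (section 3.12), and Table 3 is the only precision the plan states for it. Two features make the table look better than the design.

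First, a multiplier of 1.96 treats the SD as known. Here it will be estimated from 5 or 10 people; section 8.1 lists the SD among the statistics to be calculated.

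Second, the table is titled for the LS antibodies but takes its SDs from the parental ones. It holds the spread fixed while the mean rises about three- to four-fold, and gives no reason. Section 8.2 uses VRC01LS to set its expected half-lives but not the SD reported with it.

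Section 3.10 hypothesises longer half-lives than the parental antibodies. A reader judging that comparison would rely on this table.

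**Working it through.** **Reproducing Table 3.** Margin = 1.96 × SD/√n.
- n = 5: 1.96 × 4.5/√5 = 3.94; 1.96 × 6.5/√5 = 5.70.
- n = 10: 1.96 × 4.5/√10 = 2.79; 1.96 × 6.5/√10 = 4.03.

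All ten cells match after rounding. Two-sided t, one-sided z and one-sided t do not reproduce them.

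**Step 1: change the quantile only.** The multipliers are t(0.975, 4) = 2.776 and t(0.975, 9) = 2.262.

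| SD (days) | n = 5 stated | n = 5 with t | n = 10 stated | n = 10 with t |
|---|---|---|---|---|
| 4.5 | 3.9 | 5.6 | 2.8 | 3.2 |
| 5 | 4.4 | 6.2 | 3.1 | 3.6 |
| 5.5 | 4.8 | 6.8 | 3.4 | 3.9 |
| 6 | 5.3 | 7.5 | 3.7 | 4.3 |
| 6.5 | 5.7 | 8.1 | 4.0 | 4.6 |

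The margins widen by 2.776/1.96 = 1.42 at n = 5 and 2.262/1.96 = 1.15 at n = 10. An interval of mean ± 1.96 × sample SD/√n would cover 87.8% at n = 5 and 91.8% at n = 10.

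Table 4, in the same section, does use small-sample t methods. Its effect size at n = 4 is 2.13, whereas a normal approximation would give (1.96 + 0.84)/√4 = 1.40.

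**Step 2: check the SD against the expected mean.**
- Implied by Table 3: from 4.5/90 = 5% to 6.5/70 = 9%.
- Parental antibodies given alone (section 8.2): 6.6/24 = 27.5%, 4.9/12.8 = 38.3%, 5.7/17.6 = 32.4%, 2.9/9.6 = 30.2%.
- VRC01LS (section 3.4): 18/71 = 25.4%.
- Parental antibodies in combination, HIV-uninfected (section 3.7): 2.5/18.4 = 13.6% and 1.5/22.3 = 6.7%.

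**Step 3: margins with t under different SD assumptions.** Margin = 2.776 × SD/√5 or 2.262 × SD/√10.

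| Assumption | SD (days) | n = 5 | n = 10 |
|---|---|---|---|
| VRC01LS SD | 18 | ±22 | ±13 |
| 3 × viremic 3BNC117 SD (3 × 2.9) | 8.7 | ±10.8 | ±6.2 |
| 3 × viremic 10-1074 SD (3 × 4.9) | 14.7 | ±18.3 | ±10.5 |
| Combination CV 13.6% at 70 days | 9.5 | ±11.8 | ±6.8 |
| Combination CV 6.7% at 90 days | 6.1 | ±7.5 | ±4.3 |

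Every row exceeds the largest stated entries (5.7 and 4.0). In the last row the SD lies inside Table 3's range, so the excess there comes from the quantile alone.

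**Step 4: the fold change.** Three-fold gives 3 × 17.6 = 52.8 and 3 × 24 = 72 days from the HIV-uninfected means, and 3 × 9.6 = 28.8 and 3 × 12.8 = 38.4 days from the viremic means. Reaching 70 and 90 days takes 70/17.6 = 3.98-fold and 90/24 = 3.75-fold on the HIV-uninfected means. That agrees with the 3.9-fold reported for 3BNC117-LS in section 3.8.

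**The case against.** **The margins are conditional on a stated SD.** Each row gives its SD and the text discloses the source. If that SD were the true one and the data normal, a fixed margin of 1.96 × SD/√n would cover 95%. A reader might infer that Table 3's own margins cover only 88% and 92%. They do not: those figures describe an interval built from the sample SD. Section 8.1 does not commit to such an interval for half-life; it mentions interval estimates only for adverse events. This stands, and limits the first point to an optimistic planning convention at very small n.

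**Low variability is possible.** The section 3.7 data come from the two antibodies given together. At three-fold viremic means, those CVs give SDs of 28.8 × 0.136 = 3.9 and 38.4 × 0.067 = 2.6 days. The margins with t are then ±4.9 and ±3.2 at n = 5, and ±2.8 and ±1.8 at n = 10, no wider than the table's span. So the tempting conclusion that the design cannot achieve 3 to 6 days is not established. However, this needs HIV-uninfected CVs combined with half-lives far shorter than those section 8.2 expects.

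**The 70 and 90 days have a source.** A reader might infer from the three-fold arithmetic that they are unfounded. Section 8.2 cites preliminary human LS data, and section 3.8 supplies them. What remains is loose wording and an unstated population. No cell of Table 3 uses the fold change.

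**Little depends on the table.** Section 8.1 calls the study exploratory and primarily descriptive. This stands, and bears on severity.

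**Conclusion.** Table 3 is too favourable at the half-lives the protocol itself expects. The quantile part is exact arithmetic: the margins are 42% wider at n = 5 and 15% wider at n = 10 with t. The SD part is usually larger but rests on an assumption, because the documents give no SD for 3BNC117-LS or 10-1074-LS. Across the assumptions tabulated above, the margin is about ±7.5 to 22 days at n = 5 and ±4.3 to 13 days at n = 10. The upper end borrows the SD of a different antibody in HIV-uninfected adults; the lower end uses the smallest CV in the documents.

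This is a should-fix. The effect is overstated precision for a primary PK outcome. It does not show that 5 to 10 participants is the wrong number, and it affects no test or decision rule.

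**What to change.** - Recompute Table 3 with t on n−1 degrees of freedom, and say so in a footnote.
- Extend the SD rows to the LS scale, for example about 6 to 25 days, and give the CV and mean half-life behind each row. With t, that range gives ±7.5 to 31.0 days at n = 5 (2.776 × SD/√5) and ±4.3 to 17.9 days at n = 10 (2.262 × SD/√10). State that no SD is yet available for either LS antibody.
- In the text, replace the three-fold derivation with the preliminary data in section 3.8 (about 3.9-fold for 3BNC117-LS). Say that 70 and 90 days are HIV-uninfected expectations and that half-lives may be shorter in viremic participants, as they were for both parental antibodies.

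The cost is one table and a few sentences in section 8.2. The stated precision becomes less favourable; sample size and conduct do not change.
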